8.7 Strategies to Promote Retention

We will utilize the following strategies to promote study retention: 1) Participating families will receive a \$20 gift card at enrollment and an additional \$20 gift card for answering each subsequent study-related survey (\$100 in total); 2) We will use multiple methods of contact for parents, including home and cell phone numbers and email addresses. 3) Parents will provide days and times when a phone call is most convenient.

9 Data Analysis

9.1 Intent-to-Treat (ITT) population

Analyses will be conducted in an intention-to-treat (ITT) manner, in which all randomized subjects are included and analyzed according to their randomization assignment.⁶⁴ Subjects who withdraw or get removed from the study will be included in the ITT population. The ITT population will be used for the primary analysis as well as for safety analyses.

9.2 Multiple Comparisons

The studywise Type-1 error will be controlled by designating a single primary outcome, defined as all-cause hospital readmission within 14 days of discharge. The primary analysis will test the noninferiority of a recommendation for PRN follow-up compared to a recommendation for automatic follow-up on hospital readmission within 14 days of hospital discharge using a 1-sided α -level of 0.05.

The trial design also includes two secondary outcomes, the occurrence of a medical intervention, and health-related child quality of life as measured by the Impact on Activities and Routines instrument. We will evaluate both of these secondary outcomes for treatment efficacy using 2-sided hypothesis tests. We will use the Bonferroni-Holm procedure to assure a studywise α -level of 0.05 for the two

secondary outcomes considered jointly. In the Bonferroni-Holm procedure, we will first compute 2-sided p-values for both secondary outcomes. If the smaller of the two p-values is < 0.025, the treatment comparison for that outcome will be declared statistically significant, and the larger p-value will be compared to 0.05 to determine if the other comparison is also statistically significant. If the smallest of the two p-values is ≥ 0.025 , then the treatment comparisons for both secondary outcomes will be regarded as not statistically significant.

To avoid reducing statistical power, comparisons of safety outcomes will be performed using 2-sided α -levels of 0.05 for each safety outcome on a comparisonwise basis, without adjustment for multiple comparisons.

All other outcomes are exploratory.

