9.3 Analysis of the primary outcome

The risk of all-cause hospital readmission within 14 days of hospital discharge will be compared between the groups who receive a recommendation for PRN vs. automatic follow-up by applying maximum likelihood estimation under a log binomial generalized linear model with indicator variables for randomized treatment, the four infection types, and hospital site included in the models as predictor variables. The primary results will be expressed as a risk difference with a 95% upper confidence bound. In the event that log binomial model fails to converge, the risk ratio with the 95% upper confidence bound will be estimated by applying logistic regression (with a logistic link function) and using the marginal means approach to estimate the risk of the outcome first setting the treatment variable to "automatic" for all patients and then setting the treatment variable to "PRN" for all patients, and performing statistical inference using bootstrap resampling.

The test of noninferiority will be performed by constructing a 95% upper confidence bound for the difference in risk of a hospital readmission within 14 days under the as-needed treatment group vs. automatic follow-up group. Noninferiority will be inferred if this confidence bound excludes the noninferiority margin of 2.5%.

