9.9 Sample Size and Power

The RCT will be powered for non-inferiority of a recommendation for PRN follow-up compared to automatic follow-up for the primary outcome, 14-day all-cause hospital readmission. In 2019, the mean 14-day all-cause readmission rate across FAAN-C sites among patients who would meet inclusion criteria for FAAN-C was 3.5% (extracted from the Pediatric Health Information Systems database on April 29, 2020). Given that automatic post-hospitalization follow-up is recommended to the majority of hospitalized children, we used 3.5% as the estimated readmission rate for the automatic post-hospitalization follow-up group. We set the non-inferiority margin at 2.5% because hospitalists and PCPs reported in focus groups that they would consider a recommendation for PRN follow-up to be inferior to a recommendation for automatic follow-up if the PRN follow-up recommendation resulted in a more than 2–3% absolute increase in hospital readmissions. At a margin of 2.5%, the parents of 40 children would need to be instructed to have automatic follow-up visits before 1 hospital readmission would be prevented (that is, the number needed to treat⁷¹ =40). If \geq 40 parents would need to be instructed to have automatic follow-up to prevent a hospital readmission, we will conclude that a recommendation for PRN follow-up is non-inferior to a recommendation for automatic follow-up. We assume that the primary outcome will be available

for at least 85% of subjects (15% attrition). Under these assumptions, a total sample size of 2,674 patients (1,337 patients in each group) will provide 90% power with 1-sided α =0.025 to demonstrate non-inferiority of a recommendation for PRN follow-up. We defined the non-inferiority margin without adjusting for non-compliance for two main reasons. First, patients randomized to a recommendation for PRN follow-up are compliant whether or not they choose to attend a follow-up visit. Secondly, the assumed readmission rate for the automatic follow-up group (3.5%) is derived from a sample from which non-compliance occurred. Non-compliance is expected to be greater outside of a trial setting, which preserves our conservative power estimate.

10 Data Management

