12.1 Data Safety Monitoring Board (DSMB)

The study will have a Data Safety Monitoring Board (DSMB). The DSMB will have a charter, will approve the protocol prior to implementation, and will review interim analyses as applicable. The purpose of the DSMB is to advise the sponsors and Principal Investigator(s) regarding the continuing safety of study subjects and the continuing validity and scientific merit of the study. The DSMB is responsible for monitoring accrual of study subjects, adherence to the study protocol, assessments of data quality, performance of individual site, review of serious adverse events and other subject safety issues. There will be no formal stopping rules for efficacy or futility.

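### The primary non-inferiority test is set at one-sided 0.05 (Protocol 9.2 and 9.3), but the trial is sized at one-sided 0.025 (Protocol 9.9)

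*Protocol*

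**What the plan says.** Three sections of the protocol fix the error level of the primary comparison.

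- **Section 9.2 (Multiple Comparisons)** controls the studywise error through a single primary outcome and tests non-inferiority on "hospital readmission within 14 days of hospital discharge using a 1-sided α -level of 0.05".
- **Section 9.3 (Analysis of the primary outcome)** gives the decision rule: "The test of noninferiority will be performed by constructing a 95% upper confidence bound for the difference in risk". It continues: "Noninferiority will be inferred if this confidence bound excludes the noninferiority margin of 2.5" percent. A 95% one-sided bound corresponds to one-sided 0.05, so 9.3 agrees with 9.2.
- **Section 9.9 (Sample Size and Power)** takes the same outcome and margin and says that 2,674 patients "will provide 90% power with 1-sided α =0.025 to demonstrate non-inferiority of a recommendation for PRN follow-up".

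Section 12.1 adds: "There will be no formal stopping rules for efficacy or futility".

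**The concern.** The two levels apply to the same hypothesis, outcome and margin, so only one can be the level of the test. This is also the trial's only confirmatory decision: section 9.2 rests the whole control of type I error on it, and section 5 says that success, with similar safety outcomes, would make PRN follow-up generally preferred.

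If the analysis follows 9.2 and 9.3, it accepts about twice the risk of a false non-inferiority claim that the sample size was built on. If the observed excess falls between the two bounds, the trial succeeds under the analysis sections but misses the level quoted in the sample size section. Settling the level after such a result is known would be hard to defend.

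**Working it through.** **Inputs.** From 9.9: automatic-arm rate 3.5% ("we used 3.5% as the estimated readmission rate for the automatic post-hospitalization follow-up group"), margin 2.5 points, 90% power, primary outcome available for 85%, total 2,674 (1,337 per group). From 7.1: 1:1 allocation. Assumption: the true PRN rate is also 3.5%. The protocol does not say so, but the exact match in step 1 supports it.

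**1. Reproducing the stated size.** Evaluable n per arm = (z_α + z_0.90)² × 2 × 0.035 × 0.965 / 0.025², with z_0.90 = 1.282; then divide by 0.85.

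| One-sided α | z_α | n evaluable per arm | Randomized per arm | Total |
|---|---|---|---|---|
| 0.025 | 1.960 | 1,135.6 → 1,136 | 1,336.5 → 1,337 | **2,674** |
| 0.05 | 1.645 | 925.6 → 926 | 1,089.4 → 1,090 | **2,180** |

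So the 0.025 in 9.9 is no slip of the pen: it is the level behind the stated number. Other formulas for 90% power at one-sided 0.05 (Farrington-Manning 2,302; continuity-corrected about 2,364) do not give 2,674 either.

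**2. Power of each rule at the planned size.** SE = √(2 × 0.035 × 0.965 / 1,136) = 0.00771, and power = Φ(0.025/SE − z_α), where 0.025/SE = 3.242.

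- At 0.025: Φ(3.242 − 1.960) = Φ(1.282) = 90.0%.
- At 0.05: Φ(3.242 − 1.645) = Φ(1.597) = 94.5%.

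**3. How often the verdict depends on the level.** Exact binomial enumeration, unadjusted Wald upper bound, 1,136 per arm, 3.5% on automatic follow-up:

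| True PRN excess | Passes at 0.025 | Passes at 0.05 | Verdict differs |
|---|---|---|---|
| 0 | 89.9% | 94.4% | 4.4% |
| 1 point | 44.9% | 57.5% | 12.6% |
| 2.5 points (the margin) | 2.7% | 5.3% | 2.6% |

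The last row is the false non-inferiority rate. With equal arms, the differing-verdict probability is 1.8%, 4.4% and 7.2% at automatic-arm rates of 2.5%, 3.5% and 4.5%; with PRN one point worse it is 11.4%, 12.6% and 12.3%.

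**4. The window in observed terms.** With 3.5% observed on automatic follow-up and the SE taken at the observed rates, the largest excess that passes is about 0.90 points at 0.025 and 1.14 points at 0.05. With the SE fixed at 3.5% in both arms, it is 2.5 − 1.960 × 0.771 = 0.99 and 2.5 − 1.645 × 0.771 = 1.23. The window is about 0.24 points wide either way.

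In counts, with 40/1,136 readmissions on automatic follow-up, the largest passing PRN count is 50 at 0.025 and 52 at 0.05, so 51 or 52 changes the verdict.

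**5. Innocent explanations.**

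- *Alpha spent or split:* 12.1 has no formal efficacy or futility stopping rules, and 9.2 has one primary outcome.
- *The bound in 9.3 is really the upper limit of a two-sided 95% interval:* section 9.4 says two-sided when it means two-sided, and on this reading 9.2 would still conflict with 9.9 and would conflict with 9.3 as well.
- *Left to the analysis plan:* the protocol does not leave the level open. It fixes it at two values.

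**The case against.** The strongest reply is that the operative rule is clear. The section on type I error names 0.05, the section on the primary analysis implements it, and 9.9 uses 0.025 only as a planning input without setting a second success criterion. On that reading a result in the window simply passes, the test runs close to its own nominal 5%, and the trial is larger than it needs to be, which harms neither power nor the estimate. Two sections support 0.05 against one for 0.025, so the smallest edit would be to 9.9.

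Much of this stands. An analyst who follows 9.2 and 9.3 has one rule to apply, power is not at risk, and the documents themselves do not show that 0.025 was the intended level. But the reply does not explain why 494 more patients (2,674 − 2,180) were planned than the written test needs for its stated power, and it leaves 9.9 attaching a different alpha to the same demonstration of non-inferiority.

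A second objection is that the magnitudes are conditional. The plan adjusts for infection type and site, and imputes missing outcomes in all randomized children. With full information on 1,337 per arm, the differing-verdict probability falls to 2.9% with equal arms and 11.9% with PRN one point worse, and the 40-event example becomes 54 versus 57. The gap narrows but does not close.

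**Conclusion.** The contradiction is real and must be corrected. The sizing in 9.9 is right at its own alpha; the conflict is between it and the test in 9.2 and 9.3. The consequence is an unsettled type I error level for the sole confirmatory test: about 5.3% as written against 2.7% at the sizing level, with the verdict turning on the choice when the observed PRN excess is around one point.

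These figures are approximate. They assume 3.5% on automatic follow-up, 1,136 evaluable children per arm, and an unadjusted Wald bound standing in for the adjusted, imputed analysis. The contradiction itself depends on none of these assumptions.

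**What to change.** State one alpha throughout, and do so before outcome data by arm are seen. There are two ways:

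- **Preferred: one-sided 0.025.** Change the level in 9.2, and in 9.3 use a 97.5% one-sided upper bound, which is the upper limit of the two-sided 95% interval. Section 9.3 mentions a 95% upper bound three times, including in the fallback for non-convergence, and each mention must change. Section 9.9 stands as it is, with N = 2,674 and 90% power. The price is a stricter rule: the largest passing excess falls from about 1.14 to about 0.90 points.
- **Alternative: one-sided 0.05.** Keep 9.2 and 9.3, and restate 9.9 as one-sided 0.05 with about 94.5% power at N = 2,674. This edits one sentence; the price is keeping the looser error level.

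The first is preferred because it keeps the error level on which the trial was sized and costs no patients. If 0.05 was always the intended level, the second is equally coherent, and the protocol should say so. Neither changes the sample size, the margin or the data collected.

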9.3 Analysis of the primary outcome

The risk of all-cause hospital readmission within 14 days of hospital discharge will be compared between the groups who receive a recommendation for PRN vs. automatic follow-up by applying maximum likelihood estimation under a log binomial generalized linear model with indicator variables for randomized treatment, the four infection types, and hospital site included in the models as predictor variables. The primary results will be expressed as a risk difference with a 95% upper confidence bound. In the event that log binomial model fails to converge, the risk ratio with the 95% upper confidence bound will be estimated by applying logistic regression (with a logistic link function) and using the marginal means approach to estimate the risk of the outcome first setting the treatment variable to "automatic" for all patients and then setting the treatment variable to "PRN" for all patients, and performing statistical inference using bootstrap resampling.

The test of noninferiority will be performed by constructing a 95% upper confidence bound for the difference in risk of a hospital readmission within 14 days under the as-needed treatment group vs. automatic follow-up group. Noninferiority will be inferred if this confidence bound excludes the noninferiority margin of 2.5%.

9.4 Analysis of secondary outcomes

Similarly to the primary outcome, the probability of a medical intervention within 14 days of hospital discharge will be compared between the groups who receive a recommendation for PRN vs automatic follow-up by applying maximum likelihood estimation under a log binomial generalized linear model with indicator variables for randomized treatment, the four infection types, and hospital site included in the models as predictor variables. The estimated treatment effect will be expressed as a risk difference with a 2-sided 95% confidence interval. In the event that log binomial model fails to converge, the risk ratio with 95% confidence intervals will be estimated by applying logistic regression (with a logistic link function) and using the marginal means approach to estimate the risk of the outcome first setting the treatment variable to "automatic" for all patients and then setting the treatment variable to "PRN" for all patients, and performing statistical inference using bootstrap

resampling.

The mean health-related quality of life score 7 days after hospital discharge, measured by the Impact on Activities and Routines instrument, will be compared between the groups who receive a recommendation for PRN vs automatic follow-up by applying an analysis of covariance, with the baseline quality of life score, the four infection types, and hospital site included in the model as covariates. The estimated treatment effect will be expressed as a mean difference in the health-related quality of life score between the randomized groups with a 2-sided 95% confidence interval.

9.5 Analysis of exploratory outcomes

Generalized linear models with normal, gamma or lognormal, binary, binomial, and negative binomial outcome models will be used in ITT analyses to compare symmetric numeric, positively skewed numeric, dichotomous, count outcome assessed a designated number of times, and count outcomes without a fixed number of assessments, respectively, between the PRN and automatic follow-up recommendation groups.^{65, 66} Hospital site and type of infection will again be included as covariates. Effects will be expressed as a difference in means between the PRN and automatic follow-up recommendation groups for normal outcomes, as a ratio of means for gamma and lognormal continuous outcomes, as risk ratios for binary outcomes, and as rate ratios for binomial and negative binomial outcomes. As for the primary outcome, if the log binomial model fails to converge, relative risks for binary outcomes will be analyzed by applying logistic regression with the marginal means approach and bootstrap resampling. Analyses using the binomial outcome model will account for overdispersion. Several numeric outcomes will be evaluated longitudinally. For these outcomes, we will adjust for the baseline level of the outcome (measured on day 0), which improves statistical power by framing the analysis as an analysis of covariates (ANCOVA), as is recommended in randomized trials. Log-rank tests with stratification of the baseline hazard by hospital site and type of infection will compare time-to-event outcomes between groups. The log-rank test will be used to compare child symptom duration between randomized groups, with a hazard ratio estimating using Cox regression.

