Symptom duration	Proportion of participants who have completely recovered from their infection at 7 days after hospital discharge	Binary
Total additional ambulatory visits	Mean number of ambulatory visits (in-person or via telehealth) that a participant attends, apart from the post-hospitalization follow-up visit, within 30 days of hospital discharge; Ambulatory visits include clinic, urgent care, and emergency department (not resulting in hospital admission) visits.	Negative Binomial
Non-primary care ambulatory visits	Mean number of ambulatory visits (in-person or via telehealth) to non-primary care providers, within 30 days of hospital discharge; Non-primary care providers will include all providers outside of the clinic that families identify as their primary care clinic.	Negative Binomial
Parent self-efficacy	Mean self-efficacy score 7 days after hospital discharge, measured by the PROMIS self-efficacy short form ⁵⁸	Normal
Parent anxiety	Mean anxiety score 7 days after hospital discharge, measured by the PROMIS anxiety short form ⁵⁸	Normal or Gamma
Satisfaction with care	Proportion of participants who report agreeing or strongly agreeing with the statement, "I am satisfied with the medical care my child has received since hospital discharge," 7 days after hospital discharge	Binary
Telephone and electronic communications with medical providers	Mean number of telephone and electronic (excluding telehealth visits) communications with a medical provider within 14 days of hospital discharge	Negative Binomial
Well-child visits	Proportion of participants who attend a well-child visit within 6 months of hospital discharge	Binary
Immunizations	Proportion of participants who receive an immunization within 6 months of hospital discharge	Binary

Usual place of medical care	Proportion of participants who report having a usual place of medical care 6 months after hospital discharge	Binary	
Medical interventions related to the index infection	Proportion of participants who receive either a laboratory test, imaging ^b test, or a new medication related to the index infection within 14 days of hospital discharge	Binary	
Safety outcomes			
Medical errors	Proportion of parents who report that their child experienced a medical error within 14 days of hospital discharge, measured by the Family Safety Interview ⁵⁹	Binary	

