8.1 Study Schedule

A schedule of study events for each participant is outlined in Table 7. "While hospitalized" events will occur between the time of hospital admission and the time of hospital discharge.

Page 22 of 44 Protocol 1.00 ([name])

Table 7: Study Schedule

	While hos- pitalized	After hospital discharge			
		Day 7	Day 14	Day 30	Day 180
Screening	/				
Informed consent	/				
Parent interview	/				
Randomization	/				
Notify family, PCP, and inpatient team of assignment	/				
Chart review				/	
Process measure					 
Completion of a post-hospitalization follow-up		×			
Outcomes					
All-cause hospital readmissions		0	×	0	
Medical interventions		0	×	0	
Child health-related quality of life	0	×	0	0	
Cost burden		0	×	0	
Child time		0	×	0	
Parent time		0	×	0	
Symptom duration	0	×	0	0	
Total additional ambulatory visits		0	0	×	
Non-primary care ambulatory visits		0	0	×	
Parent self-efficacy	0	×		0	0
Parent anxiety	0	×		0	
Satisfaction with care	0	×			
Telephone or electronic communications with medical providers		0	×	0	
Well-child visits	0				×
Immunizations	0				×
Usual place of medical care	0				×
Medical interventions related to the index infection		0	×	0	
Medical errors		0	×	0	
Hospital readmissions related to the index infection		0	×	0	

^{/ =} task performed at the specified timepoint

^{○ =} measured at the specified timepoint

X = measured at the specified timepoint and this is the timepoint used for primary analyses

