8.3 The Parent Interview

The parent interview will obtain sociodemographic data (e.g., race, ethnicity, financial hardship) about the child and the child's parents. Baseline measurements of the outcomes that are measured during hospitalization will also be measured during the parent interview. Screening, consent, and the parent interview will occur before randomization.

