8.6 Outcome Measurement

Outcomes will be measured according to the timing in Table 7. "While hospitalized" outcomes will be measured prior to randomization. "After hospital discharge" outcomes will be measured by surveying parents on days 7, 14, 30, and 180, as specified. An additional 4 days will be permitted for the collection of data on the 7, 14, and 30 day timepoints and \pm 7 days for the day 180 timepoint. For example, day 7 outcomes can be collected between day 7 and day 11. These intervals allow for holidays, weekends, and other reasons for parent unavailability that may preclude contact on the exact day.

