9.8 Missing Data

We will use multiple imputation based on fully sequential imputation with predictive mean matching to impute missing data. Multiple imputation will be particularly useful because we expect to have strong auxiliary variables—that is, variables that are highly correlated with study outcomes and risk of missingness. Auxiliary variables we will utilize include patient demographic factors (e.g., race, ethnicity) measures of illness severity (e.g., length of stay, disease-specific characteristics), and hospital readmission documented in the electronic medical record.

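### Section 9.5 adjusts for baseline only in numeric outcomes, although three binary exploratory outcomes also have a pre-randomization value and the stated power argument covers them (low severity)

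*Protocol*

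**What the plan says.** Section 9.5 specifies generalized linear models for the exploratory outcomes, with hospital site and infection type as covariates. It then adds: "Several numeric outcomes will be evaluated longitudinally. For these outcomes, we will adjust for the baseline level of the outcome". The justification is that this raises power and is recommended in randomized trials. No such provision is made for binary outcomes.

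Table 7 (section 8.1) marks five binary outcomes as measured while the child is in hospital: symptom duration, satisfaction with care, well-child visits, immunizations, and "Usual place of medical care". Section 8.3 says: "Baseline measurements of the outcomes that are measured during hospitalization will also be measured during the parent interview". It also says: "Screening, consent, and the parent interview will occur before randomization". Section 8.6 confirms that the in-hospital "outcomes will be measured prior to randomization".

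Table 5 classes all five as binary. The third of the 6-month outcomes, for example, is the "Proportion of participants who report having a usual place of medical care 6 months after hospital discharge".

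**The concern.** For well-child visits, immunizations and usual place of care, Table 7 shows only two measurements: one in hospital and one at day 180. The in-hospital value is therefore the only other observation of the same outcome, and the protocol states no analytic use for it. An analyst who follows section 9.5 as written would leave it out, because the sentence is limited to numeric outcomes.

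The power argument does not depend on the outcome being numeric. A prognostic pre-randomization covariate also sharpens a comparison of two proportions. Section 4.4 treats these three outcomes as the place where as-needed follow-up might show a modest loss of contact with primary care, so interval width matters for telling a small loss from none. What is at stake is the precision of exploratory estimates. Bias and type I error are not in question.

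**Working it through.** **1. The plan's own figure.** Section 9.9 inputs are 3.5% readmission in both groups, margin 2.5%, one-sided alpha 0.025, 90% power and 15% attrition.

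- Per group: (1.960 + 1.282)² × 2 × 0.035 × 0.965 / 0.025² gives 1,136 evaluable.
- Inflated: 1,136 / 0.85 gives 1,337, or 2,674 in total. This matches.

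The figure rests on readmission, which has no baseline value, so it does not move. Below, 1,136 per group is borrowed only for illustration, because the protocol states no retention figure for day 180.

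**2. Which baseline values are usable.** Of the five binary outcomes, two drop out. Recovery is nearly constant among children still in hospital. Satisfaction is worded "I am satisfied with the medical care my child has received since hospital discharge", which has no identical item before discharge. Well-child visits, immunizations and usual place of care remain.

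**3. Formula.** With 1:1 allocation, adjusting a marginal risk contrast for a baseline binary variable multiplies its variance by 1 − phi². Interval width is multiplied by √(1 − phi²). Phi is the correlation between baseline and follow-up, strictly what remains after site and infection type. The protocol does not give it, so the range is an assumption.

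| Assumed phi | Variance ratio | Interval narrower by | 80% power becomes |
|---|---|---|---|
| 0.1 | 0.99 | 0.5% | 80.4% |
| 0.2 | 0.96 | 2.0% | 81.6% |
| 0.3 | 0.91 | 4.6% | 83.6% |
| 0.5 | 0.75 | 13.4% | 89.9% |
| 0.7 | 0.51 | 28.6% | 97.5% |

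A simulation (1,136 per group, 4,000 replicates, risks standardized over baseline strata) gave variance ratios of 0.975, 0.898 and 0.723 at phi 0.17, 0.33 and 0.53. The formula predicts 0.970, 0.893 and 0.720.

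**4. In percentage points.** At a risk of 0.90, the unadjusted 95% half-width for a risk difference is 1.96 × √(2 × 0.90 × 0.10 / 1,136) = 2.47 points. With adjustment it is 2.35 (phi 0.3), 2.14 (phi 0.5) or 1.76 (phi 0.7). Section 9.5 reports risk ratios for binary outcomes; for the ratio of standardized risks the proportional gain is the same to first order.

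**5. Usual place of care.** Let q be the baseline prevalence, p1 and p0 the day-180 risks by baseline status, and p = q·p1 + (1 − q)·p0. Then phi² = q(1 − q)(p1 − p0)² / [p(1 − p)]. Assume p1 = 0.97 and p0 = 0.60:

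- q = 0.90: p = 0.933, phi² = 0.0123 / 0.0625 = 0.197, worth 1/(1 − 0.197) or about 25% more patients.
- q = 0.98: p = 0.963, phi² = 0.00268 / 0.0360 = 0.075, about 8%.
- q = 0.99: p = 0.966, phi² = 0.00136 / 0.0326 = 0.042, about 4%.

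Table 6 excludes children for whom no clinic for follow-up can be identified, so the higher prevalences are the more plausible ones.

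**6. Well-child visits and immunizations.** If 60% are positive at baseline and day-180 risk is 65% against 30% (assumed), p = 0.51 and phi² = 0.24 × 0.1225 / 0.2499 = 0.118, worth about 13% more patients. Nothing in the documents supports or rules out this split.

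**The case against.** The strongest reply is that nothing in section 9.5 is invalid. Treatment, site and infection type respect the stratified randomization, and an extra prognostic covariate is an efficiency preference. The outcomes are exploratory with no power claim, and covariate lists for such outcomes are often left to a statistical analysis plan. This stands as a limit on severity. It does not remove the point, because section 9.5 does state a baseline-adjustment rule and confines it to numeric outcomes.

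A second reply is that the protocol does not say what the in-hospital well-child and immunization questions ask, so they may not measure the same construct as an event in the following 6 months. That also stands, and is why the fix is conditional. A third is that more covariates make a log-binomial model less likely to converge, especially with sparse baseline cells. That is true but small, since section 9.5 already supplies a logistic fallback.

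A reader might go further and infer that section 9.8 also wastes data, because it names no other survey wave for imputation. The text does not support this. It says: "Auxiliary variables we will utilize include patient demographic factors (e.g., race, ethnicity) measures of illness severity (e.g., length of stay, disease-specific characteristics", and the verb leaves the list open. Its criterion, strong correlation with outcomes and with missingness, admits the other surveys. Baseline quality of life is already in the section 9.4 model. The gain would also be small: at 15% missing and an assumed correlation of 0.6, the interval would be about 2.7% narrower.

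**Conclusion.** The point holds as a low-severity improvement. Section 9.5 withholds baseline adjustment from three binary exploratory outcomes whose baseline values are already scheduled, for a reason that covers them equally. The benefit runs from negligible (0.5% narrower at phi 0.1) through modest (4.6% at 0.3) to material (13.4% at 0.5), and rests wholly on correlations that must be assumed.

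A reader might infer a gain like a quarter more patients for usual place of care. That needs 10% of enrolled children to lack a usual place at baseline, which sits poorly with the exclusion in Table 6. At 2% the gain is about 8%.

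Nor is any confirmatory result touched. Readmission and medical interventions have no baseline value in Table 7, quality of life is already adjusted for baseline, and 2,674 is unchanged.

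**What to change.** In section 9.5, extend the baseline-adjustment sentence to binary outcomes. For well-child visits, immunizations and usual place of medical care, add the in-hospital value from Table 7 as a covariate wherever it measures the same construct as the day-180 outcome and is not nearly constant. Judge near-constancy on pooled data, without reference to treatment group, by a threshold set beforehand. State that the existing logistic and marginal-means fallback applies if the log-binomial model does not converge.

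The cost is one sentence and minor code, with no new data collection. The drawback is a somewhat higher chance that the fallback is needed. Section 9.8 needs no change on this account.
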